## 1 INTRODUCTION

This Statistical Analysis Plan (SAP) for Final Analysis (FA) describes the procedures and timeline for the Final Analysis specified in the protocol TA799-101 5.0, FINAL, 27/MAR/2023 ([VectivBio AG 2023](#)). For the rationale and aim of the trial, please refer to the *protocol* for details. The Final analysis will be done in two steps. The Primary analysis of safety and efficacy will be performed once all subjects have either completed Day 91 or withdrawn from the trial. Additional analyses will be done once all the subjects have either completed the end of trial (EOT) visit or withdrawn from the trial. This additional analysis will be referred to as “EOT analysis”.

The Primary Analysis targets the characterization of the safety profile and the obtention of efficacy results. It will be used to support the Clinical Trial Report (CTR). The EOT analysis will feed an addendum to the CTR that will cover the follow-up period until 2 years after the first apaglutide dose.

All decisions regarding Primary analysis, as defined in the present SAP document, have been made prior to database snapshot for the Primary analysis. This SAP FA consists of an extension of the SAP of the Interim Analysis (IA) performed for this trial.

The clinical cut-off date for the Primary analysis will be when all enrolled subjects have either reached Day 91 or withdrawn from trial: up to 01 Dec 2023 (included). All available data points by the clinical cut-off date will be included in the Primary analysis; at the time of the data extract, all data points after the clinical cut-off date will be programmatically cut. Data extracted from the electronic data capture (EDC) system and data transferred from external vendor sources (e.g., lab data) will be mapped into the Study Data Tabulation Model (SDTM, v1.7 and implementation guidelines SDTMIG 3.3) datasets which will be used as the source data for the Primary analysis. Note that the technical procedures and steps for processing these data and for implementing the definitions of variables for the purpose of the statistical analysis are covered in the analysis datasets specifications document (programming cut-off, analysis data model, ADaM, v2.1 and implementation guidelines ADaMIG 1.2).

The Final Analysis will be performed under single-blind design of the trial. Actual treatments will be mapped into the SDTM. Details of the unblinding procedure are described in the Trial Blinding Plan.

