Unless specified otherwise, endpoints described in this document will be analyzed at both analysis steps: Primary Analysis and EOT Analysis.

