#### *4.3.9.15 Lower GI-aGVHD flare up to Day 182 up post-first dose of apraglutide*

The lower GI-aGVHD flare up to Day 182 rate is defined as the proportion of subjects experiencing a lower GI-aGVHD flare between the end of treatment due to CR and 182 days after the first dose of apraglutide. The denominator for the proportion is the number in the FAS. The number and percentage of subjects with lower GI-aGVHD flare up to Day 182 will be provided by apraglutide dose levels and in total along with the corresponding two-sided 95% confidence intervals using Clopper-Pearson exact method.

If 5 subjects or less experienced a lower Gi-aGVHD flare at the clinical cut-off date, the analysis of the lower GI-aGVHD flare data will be restricted to a listing of data related to flare.

*4.3.9.16 Graft Failure up to 2 years post-first dose of apaglutide*

Graft failure are collected in the AE form.

The graft failure time is defined as the time from the date of transplant to the date of the graft failure.

The graft failure will be summarized using Kaplan-Meier estimator. The number and percentage of subjects experiencing an event, and subjects censored will be summarized by apaglutide dose levels and in total. The median time-to-event will be presented where possible, along with the range and the associated two-sided 95% Brookmeyer-Crowley confidence interval. The event-free rate with 95% CI using Greenwood's formula will be provided for selected time points (e.g., 1, 3, 6, 12 and 24 months).

Plots of the Kaplan-Meier estimate for the graft failure will be presented by apaglutide dose levels and in total.

Subjects who are alive at the time of data cut-off and for which no graft failure event occurs will be right censored at their last follow-up visit.

Graft failure will be analyzed only for the EOT analysis.

*4.3.9.17 Infections and Sepsis from baseline to Day 91 and overall*

Infections and sepsis will be derived programmatically from AEs coded using MedDRA based on Sponsor-defined list (see Table 4-4).

The number and percentage of subjects experiencing infections and sepsis starting between the first dose of apaglutide up to Day 91 and until the end, as well as starting between the first dose of apaglutide up the end of the study, will be provided by apaglutide dose levels and in total.

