#### *4.3.10.7 Hospitalization up to Week 26*

The initial hospitalization is defined as the hospitalization for which Day 1 is comprised between date of admission and date of discharge.

The initial time to discharge from hospital is computed as time of discharge of the initial hospitalization - date of admission of the initial hospitalization + 1 Day.

The time to discharge from hospital up to Week 26 is defined as the sum of the time to discharge from any hospitalization which occurred between Day 1 and Day 182. The following rules will be applied to derive the individual time to discharge from a hospitalization:

- If a hospitalization started before Day1, the date of admission will be set to Day 1
- If a hospitalization ends after Day 182, or if end date is missing, the date of discharge will be set to Day 182
- The time to discharge from a hospitalization is then derived as  
time of discharge - date of admission + 1 Day

The number of readmission up to Week 26 is defined as the number of hospitalization, different from the initial hospitalization, which occurred between Day 1 and Day 182.

The duration of readmission up to Week 26 is defined as the sum of the time to discharge from any hospitalization which occurred between Day 1 and Day 182, except from the initial hospitalization.

The time to discharge from hospital up to Week 26, the number of readmissions up to Week 26 and the duration of readmission up to Week 26 following hospitalization data from Day 1 to Day 182 will be summarized descriptively by apaglutide dose levels and in total.

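### At the Primary Analysis, the Day 182 flare proportion and Week 26 hospitalization measures ignore 182-day windows still open at the cut-off: flare and readmission count come out low, and readmission duration and total hospital time are distorted in an unknown direction

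*SAP*

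**What the plan says.** **Timing.** SAP Section 1: "The Primary analysis of safety and efficacy will be performed once all subjects have either completed Day 91 or withdrawn from the trial". The clinical cut-off is 01 Dec 2023, and "at the time of the data extract, all data points after the clinical cut-off date will be programmatically cut".

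**Which analysis reports what.** SAP Section 1 sets a default: "Unless specified otherwise, endpoints described in this document will be analyzed at both analysis steps: Primary Analysis and EOT Analysis". Sections 3.2 and 3.3 tag several endpoints as EOT-only or Primary-only. Flare up to Day 182 (3.2) and the Week 26 hospitalization endpoint (3.3) carry neither tag, and Sections 4.3.9.15 and 4.3.10.7 add no restriction.

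**Flare (4.3.9.15).** The numerator is subjects who flare between stopping for CR and 182 days after first dose. "The denominator for the proportion is the number in the FAS", with a Clopper-Pearson interval. If 5 or fewer subjects have flared at the cut-off, only a listing is produced.

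**Hospitalization (4.3.10.7).** "The number of readmission up to Week 26 is defined as the number of hospitalization, different from the initial hospitalization", occurring between Day 1 and Day 182. Duration of readmission and total time in hospital are sums over the same window. A stay that ends after Day 182, or has no end date, is given Day 182 as its discharge date. Nothing is said about subjects whose follow-up at the cut-off is shorter than 182 days.

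**The concern.** With a Day 91 trigger and a 182-day window, recently dosed subjects have only part of their window observed. For flare, the fixed FAS denominator scores the unobserved part as flare-free. For readmissions, the same follows from a plain count with no censoring or exposure rule. The SAP does not say that such subjects are event-free; this is the result of applying its rules as written.

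The Clinical Trial Report is written from the Primary Analysis, and the EOT Analysis feeds only an addendum. A figure labelled as covering Day 182 or Week 26 would therefore rest on incomplete windows. The flare proportion and readmission count would then rise at EOT merely because follow-up had completed. Flare after stopping for CR bears on how durable the response is, so a reader of the first report could draw too favourable a picture.

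**Working it through.** The documents state no flare rate, readmission figure or precision target for these endpoints, so there is no plan figure to reproduce.

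**1. Which windows are open** (cut-off date from SAP Section 1)
- Day 182 reached by the cut-off: 01 Dec 2023 − 182 days = first dose by 02 Jun 2023.
- Day 91 reached by the cut-off: 01 Dec 2023 − 91 days = first dose by 01 Sep 2023.
- Subjects dosed from 03 Jun to 01 Sep 2023 meet the trigger with an open window. (Analysis-day numbering in SAP 4.1.1 can shift this by one day.)

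**2. Whether another rule covers it**
- SAP 4.3.9 removes visits due after the cut-off from the denominator. It concerns scheduled visits, while flare is a cumulative event with its own stated denominator. Hospitalization sits outside 4.3.9.
- SAP Section 6, item 9 right-censors duration of response for subjects short of 182 days. It names only that endpoint, but it shows that such subjects were expected.

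**3. Share of the window observed in a subject cut at Day 91**
- Flare, stopped for CR at Day 56: (91 − 56)/(182 − 56) = 35/126 = 28%. Stopped at Day 91: 0/91 = 0%.
- Readmissions: 91/182 = 50%.

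**4. Effect by number of open windows, k**

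Assumptions: FAS of 34, constant event rate, flare risk from Day 56. Ratio of reported to complete-window value = (34 − k + k × s)/34, where s is the share observed. With follow-up of open subjects spread evenly over Days 91–182, s averages 0.639 for flare and 0.75 for readmissions. If all are at Day 91 exactly, s is 0.278 and 0.50.

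| k | Flare, even spread | Flare, all at Day 91 | Readmission count, even spread | Readmission count, all at Day 91 |
|---|---|---|---|---|
| 1 | 0.99 | 0.98 | 0.99 | 0.99 |
| 5 | 0.95 | 0.89 | 0.96 | 0.93 |
| 10 | 0.89 | 0.79 | 0.93 | 0.85 |
| 17 | 0.82 | 0.64 | 0.88 | 0.75 |

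**5. Effect under assumed accrual**
- Uniform accrual to 01 Sep 2023 from 25 Mar, 15 Jun or 1 Oct 2022 leaves 17%, 21% or 27% of windows open.
- If 17 subjects were dosed by 29 Mar 2023 (the interim SAP date, 24 May 2023, minus 56 days) and the rest evenly to 01 Sep 2023, the share is 25% (N = 30) to 29% (N = 34).
- Take a constant flare hazard from Day 56 or Day 91, a Day 182 risk of 20% or 40%, and follow-up even over Days 91–182. Open-window subjects then show 52–69% of their Day 182 flares.
- Relative understatement = open share × (1 − share seen): from 0.17 × (1 − 0.69) = 5% to 0.29 × (1 − 0.52) = 14%.

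**6. Duration moves both ways**

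Unobserved days count as out of hospital, which lowers the total. The end-date rule raises it. For a subject readmitted on Day 85 and still an inpatient at a Day 91 cut-off, the assigned stay is 182 − 85 + 1 = 98 days, against 91 − 85 + 1 = 7 observed.

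**7. Listing threshold**

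With N = 34, the chance of 6 or more flares is 12%, 40%, 70% and 89% at true FAS rates of 10%, 15%, 20% and 25%. The threshold is itself applied at the cut-off. At 20%, an understatement of 5% gives 0.20 × 0.95 = 0.190 and a chance of 65%. An understatement of 14% gives 0.20 × 0.86 = 0.172 and a chance of 54%.

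**The case against.** The other side has several good points.

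- **Direction.** A reader might infer that every one of these measures comes out too low. The documents do not support that for readmission duration or total time in hospital: step 6 shows the Day 182 rule can push them well above what was observed. Only the flare proportion and the readmission count have a clear downward bias.
- **The flare rate may never be shown.** With 5 or fewer flares there is only a listing. If, as an assumption, 17 of 34 subjects stop for CR, the chance of 6 or more flares is about 11% at a 20% risk and 74% at 40%. This stands as a limit. But the threshold is also affected by open windows, and the readmission count has no such threshold.
- **Size.** At a 20% flare rate, 5–14% relative is 1.0–2.8 percentage points. By comparison, 7/34 = 20.6% has a 95% interval of 8.7–37.9%. The effect is small beside sampling error. It is nevertheless systematic and avoidable.
- **Accrual is assumed.** The 15 Jun and 1 Oct 2022 starts have no source in the documents, and the interim SAP date need not be the interim data cut. The open share also counts late-dosed subjects who died before the cut-off or never stopped for CR. The magnitude is therefore illustrative.
- **Other evidence on durability.** The Primary Analysis also gives durable lower GI response from Day 56 to Day 91 and a Kaplan-Meier duration of lower GI response. Flare is one of many secondary endpoints and hospitalization is exploratory. That limits the consequence, but does not make the labelled figures right.

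**Conclusion.** The point holds in this form. At the Primary Analysis the SAP has no rule for 182-day windows still open at the cut-off. The flare proportion, when shown, and the readmission count are then biased low. Readmission duration and total time in hospital are biased in an unknown net direction.

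The size depends on how many subjects were first dosed after 02 Jun 2023, which the documents do not give. With 17–29% of windows open and a constant flare hazard, the flare rate is about 5–14% too low in relative terms. Because the trigger is the last subject's Day 91, at least one open window is likely.

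A reader might also infer that the final results are affected. They are not affected by this problem: it is confined to the Primary Analysis and its report, and resolves at the EOT Analysis. Whether subjects never at risk of flare belong in the FAS denominator is a separate question.

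**What to change.** In SAP 3.2, 3.3, 4.3.9.15 and 4.3.10.7, restrict to the EOT Analysis the flare rate and all Week 26 hospitalization measures: time to discharge up to Week 26, and number and duration of readmissions.

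If figures are wanted at the Primary Analysis, there are two alternatives:
- Restrict these measures to subjects first dosed at least 182 days before the cut-off. The restriction is by calendar date, so it does not depend on outcome.
- Report flare as cumulative incidence with administrative censoring at the cut-off. Protocol 7.8.2 already provides for cumulative incidence where there are competing risks.

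In either case, do not extend stays that are ongoing at the cut-off to Day 182.

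The cost is a tag or a sentence in each section, with no new data. The downside is that these figures move to the addendum, or rest on fewer subjects in the first report (about 71–83% under the accrual assumptions above, that is, 100% minus 29% to 17%).

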**Table 4-4 Sponsor-Defined Infections and Sepsis terms. SMQ = Standardised MedDRA Queries**

Infections	SMQ: 20000234 Sepsis
Sepsis	SOC: Infections and Infestations

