- Cumulative SS and RUX doses from start of the RUX treatment up to Day 91 after the first dose of apaglutide
- Incidence of infections and sepsis from baseline to Day 91 after the first dose of apaglutide
- Effect of the two dose groups on safety/tolerability and efficacy

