5.8.6 Adverse Events

Adverse events will be recorded in the AE pages of the eCRF for all eligible subjects. During screening only SAEs or trial related AEs will be reported. Once eligibility is confirmed all AEs will be reported in the eCRF. Adverse events will be reported using a recognized medical term or diagnosis that accurately reflects the event. Adverse events will be assessed by the Investigator for severity, relationship to the investigational product or a protocol requirement, possible etiologies, and whether the event meets criteria as an SAE and therefore requires immediate notification of the Sponsor. See Section 6.2 for the definition of SAEs, and Section 6.2.6 and Section 6.2.3 for guidelines for assessment of severity and relationship, respectively. If the event has not recovered to baseline or Grade 1 at the end of the trial reporting period, it will be documented as ongoing for all events that are at least possibly related to apaglutide. If an AE evolves into a condition which becomes "serious" it will be reported as an SAE.

Any laboratory abnormality will be considered an AE if it is judged to be clinically significant by the Investigator.

Infections (local as well as systemic) and sepsis events will be captured in the eCRF together with the severity and any interventions taken; they will be coded according to the version of the Medical Dictionary for Regulatory Activities (MedDRA) in use in the trial at the time.

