- Cumulative SS and RUX doses from start of the RUX treatment up to Day 91 after the first dose of apaglutide [Only for Primary Analysis]
- Incidence of infections and sepsis from baseline to Day 91 and overall after the first dose of apaglutide

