## 6 CHANGES FROM PROTOCOL-SPECIFIED STATISTICAL ANALYSES

1. Analysis Day will not include Day 0, per CDISC compliance, whereas protocol considers Day 0. The distinction between visits and analysis days is detailed in Section 4.1.1.
2. Treatment description is broken down into main treatment (W0-W7) and extension treatment (W8-W13), for analysis purpose.
3. Sample size determination explicitly refers to durable overall response on the Lower GI MAGIC score.
4. Wording of the definition of Additional systemic therapies in Appendix A has been added for completeness.
5. The AE Grading for on-sites reactions was contradictory in the protocol and is clarified in Section 4.3.8.1
6. The SAS1 and SAS2 analysis population were merged in a single analysis population, as the analysis output formatting can provide equivalent information.
7. Due to the absence of adequate historical control, the comparison to external data on BAT was not planned for the Primary Analysis.
8. Brookmeyer-Crowley confidence interval levels are set to 95% (instead of 90% in protocol) for consistency of levels between confidence intervals.
9. Duration of response from Day 28 and Day 56 on the total MAGIC score are analyzed regardless of follow-up duration, with right-censoring for subjects who did not reach the 182 days of follow-up at data cut-off.

10. The incidence of infections and sepsis from baseline are analyzed up to Day 91 but also up to the end of the trial.
11. Physical examination was added in the list of safety endpoints as the protocol states that physical examination will be analyzed as safety endpoint.
12. The following endpoint listed in the protocol was removed from the list of endpoints as no formal comparison will be performed: Effect of the two dose groups on safety/tolerability and efficacy

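### SAP Table 4-4 exchanges the MedDRA definitions of infections and sepsis, so the programmed secondary endpoint would report each under the other's name

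*SAP*

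**What the plan says.** Both documents list the incidence of infections and sepsis as a secondary endpoint. The protocol (section 1.5.2.2) has "Incidence of infections and sepsis from baseline to Day 91 after the first dose of apaglutide". The SAP (section 3.2) adds an overall period: "Incidence of infections and sepsis from baseline to Day 91 and overall after the first dose of apaglutide". SAP section 3.2 does not restrict this endpoint to one analysis step, so by SAP section 1 it is produced at both the Primary and the EOT analysis.

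SAP section 4.3.9.17 gives the derivation: "Infections and sepsis will be derived programmatically from AEs coded using MedDRA based on Sponsor-defined list (see Table 4-4"). Table 4-4 has two rows:

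- Infections: "SMQ: 20000234 Sepsis"
- Sepsis: "SOC: Infections and Infestations"

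The planned output is "The number and percentage of subjects experiencing infections and sepsis starting between the first dose of apaglutide up to Day 91", together with the period to the end of the trial, by dose level and in total. The SAP gives no other definition of either term.

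**The concern.** Each definition in Table 4-4 names the other row's label. The SOC, which collects every coded infection, defines sepsis. The Sepsis SMQ, which is meant to pick out sepsis terms, defines infections.

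The table is the operative rule for a programmed endpoint, so a programmer who follows the signed SAP reproduces the exchange in the output. Subjects here are on systemic steroids plus ruxolitinib, and safety is the primary objective. A reader would see a sepsis rate that is really the rate of any infection, and an infection rate from which ordinary infections have disappeared. The distinction also bears on the proposed mechanism, because protocol section 5.7 uses systemic infections of probable gut origin as one measure of barrier function.

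**Working it through.** The plan states no rate, power or sample size for this endpoint, so there is no figure to reproduce. The check is one of logic.

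**1. Is the mapping intended?** Protocol section 5.8.6 treats infections as the broad category and names sepsis separately: "Infections (local as well as systemic) and sepsis events will be captured in the eCRF together with the severity and any interventions taken". SAP section 6 lists the changes from the protocol. Its only entry on this endpoint is the longer window: "The incidence of infections and sepsis from baseline are analyzed up to Day 91 but also up to the end of the trial". Nothing declares or explains a reversed definition.

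**2. What does the table do if followed literally?** Classify subjects by whether they have an event in the infection SOC and whether they have an event in the Sepsis SMQ.

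| Subject's events | As written: Infections / Sepsis | Entries exchanged: Infections / Sepsis |
|---|---|---|
| In the SOC, not in the SMQ | No / Yes | Yes / No |
| In both | Yes / Yes | Yes / Yes |
| In the SMQ, not in the SOC (if any) | Yes / No | No / Yes |
| In neither | No / No | No / No |

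The line labelled Sepsis therefore equals the incidence of any infection-SOC event, and the line labelled Infections equals the incidence of Sepsis SMQ events. The two lines swap completely. A combined count (either definition met) is the same under both mappings.

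**3. Size.** Let p(inf) be the proportion with any infection-SOC event and p(sep) the proportion with a Sepsis SMQ event. Sepsis is overstated by p(inf)/p(sep), and infections are understated by the same factor. The rates below are assumptions, used only for illustration.

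- 30 randomized subjects, 21 with an infection and 3 with sepsis: 21/30 = 70%; 3/30 = 10%; ratio 70/10 = 7. The table would show sepsis 70% and infections 10%.
- Infections 50–90%, sepsis 5–20%: smallest ratio 50/20 = 2.5; largest ratio 90/5 = 18.

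**4. Can the right figures be recovered from other tables?** SAP section 4.3.8.1 tabulates AEs by SOC and PT in three periods: pre-treatment, treatment-emergent (to 28 days after the last dose) and post-treatment. A subject whose last dose is at Week 7 (Day 49) leaves the treatment-emergent period at Day 49 + 28 = Day 77. Infections starting in the remaining 91 − 77 = 14 days fall in the post-treatment table. No SOC/PT table counts subjects from first dose to Day 91, and none totals the Sepsis SMQ. Recovery is partial.

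**The case against.** The label mismatch itself is hard to dispute. The case against concerns its consequence and weight.

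- **Separate or combined.** Section 4.3.9.17 does not say whether infections and sepsis are two lines or one. A combined count would be right despite the wrong labels. This stands as a condition on the consequence, though two separately defined rows suggest two lines.
- **Unseen specifications.** Detailed programming specifications sit in another document (SAP section 5) and may already correct the slip. That is possible, but the signed SAP would remain wrong and the output would depart from it without a record.
- **PDF reading.** The table was extracted by a program, so a displaced cell cannot be wholly excluded. Both rows read as intact label-and-definition pairs, and nothing suggests a shift. A look at the original page settles it.
- **Weight.** The endpoint is descriptive, with no test or decision rule attached. The Day 56 response, the sample size and the toxicity rule in protocol section 6.6.3 do not use Table 4-4. The infection SOC and individual sepsis terms still appear under their own names in the general AE tables. All of this stands and limits the damage to this one endpoint.
- **Magnitude.** The 7-fold figure comes from assumed counts. That is so, and the finding does not depend on it.

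**Conclusion.** The concern holds: Table 4-4 is wrong as written. The definitions of infections and sepsis are exchanged in the only rule the SAP gives for a listed secondary endpoint, and nothing in either document shows this to be deliberate. If the two categories are reported separately and programmed as specified, the lines swap in both the Day 91 and the overall summaries, by a factor equal to the ratio of infection to sepsis incidence (2.5 to 18 under the assumed rates above). If only a combined count is produced, the number is right and the definitions are still mislabelled. The content of the SMQ, and whether all its terms lie within the infection SOC, cannot be checked from the documents; the conclusion needs neither.

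**What to change.** Exchange the two entries in Table 4-4, so that Infections is defined by the SOC Infections and Infestations and Sepsis by SMQ 20000234. In the same edit:

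- state whether the SMQ is applied with narrow or broad scope, as Table 4-2 does for its SMQ entries;
- state in section 4.3.9.17 whether infections and sepsis are separate lines, a combined line, or both;
- check the original table, the analysis dataset and programming specifications, and any output already produced, and record the correction.

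The core change is one line in the SAP. It needs no new data and alters no other analysis. Output already run for this endpoint would have to be rerun or relabelled if it followed the table.
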